#### **5.4.2 Categorical Secondary Effectiveness Endpoints**

##### **5.4.2.1 Total UDPB Events (by class)**

The UDPB  $\geq 2$  events (Section 3 of the CIP) will be adjudicated by Clinical Events Committee (CEC). The adjudicated events will be analyzed using the Mann-Whitney U test method stratified by class (moderate [UDPB=2], severe [UDPB=3], and massive [UDPB=4]) to assess the risk of having different severity of bleeding events between the treatment and control group.

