Additional powered secondary endpoints include 24-hour CTD (volume [mL]), total platelet transfusions (volume [mL] and units), and total PRBC transfusions (volume [mL] and units) during the index hospitalization. Twenty-four-hour CTD (mL) will be assessed via two-sample t-test for mean difference. The transfusion endpoints will all be analyzed using two-sample t-tests for mean differences, and Fisher-Freeman-Halton exact tests for units. In the event the assumptions for a two-sample t-test are not met in any of the above, a nonparametric test such as a Mann-Whitney test will be employed, with median and range values provided in the output. Other secondary endpoints include the remaining Win Ratio component parts: proportions of fatal perioperative bleeding events will be assessed via Fisher's exact test; and proportions of UDPB events (by category) will be assessed via a Fisher-Freeman-Halton exact test. The secondary endpoint of surgical re-exploration for bleeding will take into account time to re-exploration.

Sample Size

Up to 140 subjects will be randomized in a 1:1 ratio to the treatment and control arms. Sample size is based on assumed response rates for the primary effectiveness Win Ratio sub-components, and can be calculated via an iterative simulation process with programming code available in an appendix to Redfors et al. (2019).[11] With a Finkelstein-Schoenfeld test, total of 57 subjects per arm ensures power of $\geq 99.7\%$, using a two-sided alpha (α) of 0.05. With this same per arm sample size, power for the key secondary endpoint is estimated at $>99.9\%$, and for 24-hour chest tube drainage (mL), $>99.9\%$, based on a two-sample t-test assuming equal variance and a two-sided alpha of 0.05. Similarly, although assuming unequal variances, power for comparisons of platelet transfusions (volume [mL]) and PRBC transfusions (volume [mL]), is estimated at 98.0% and 96.7%, respectively.

Analysis Populations

Enrolled subjects include all subjects who provide informed assent/consent. Enrolled subjects who do not meet criteria for study eligibility are screening failures and will exit the study.

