Type I error (alpha, α) will be preserved from inflation due to multiplicity across the primary effectiveness, key secondary, and secondary endpoints via a hierarchical closed testing step-down approach. Only in the event that preceding endpoints are declared statistically significant at the alpha 0.05 level, can further endpoints also be declared significant. The order of hierarchical testing will follow the order of primary, key secondary, and secondary endpoints as listed in the paragraph above, namely: the primary endpoint will be tested first, followed by the key secondary endpoint (percent change in pre-CPB vs. post-CPB blood ticagrelor levels), followed by the first secondary endpoint (24-hour CTD), second secondary endpoint (platelet transfusions), and lastly (PRBC transfusions). Should all preceding statistical comparisons show results below their alpha cut-off values, further secondary endpoints will be evaluated: the proportion of fatal perioperative bleeding events, proportions of UDPB events (by category), and surgical re-exploration rates.

Other exploratory endpoints include:

- Area under the concentration time curve (AUC), using the trapezoidal approach, for intraoperative ticagrelor pharmacokinetic (PK) concentration
- Operative time (measured from start of skin incision to completion of chest closure)
- Duration of ICU stay
- Duration of hospital stay
- 30-day hospital re-admissions

Details on methods of analysis for exploratory endpoints will be provided in the SAP.

Further details regarding summary and analysis of effectiveness data will be provided in the SAP.

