### **3.7 Multiple Comparisons/Multiplicity**

The type I error will be controlled on the multiple outcomes on the primary and secondary effectiveness endpoints through sequential testing procedure in the following order:

Primary endpoint → Key secondary endpoint → Additional Secondary endpoints (24hr CTD → platelet transfusions → PRBC transfusions → UDPB events by class → surgical re-exploration for excessive bleeding → fatal perioperative bleeding event)

The same hierarchy will be applied to the analysis of the population of special interest (i.e., i-CABG).

The significance for the secondary endpoints will only be considered if the primary endpoint is declared statistically significant and the p-value of the previous endpoint is less than 5%, otherwise, all the subsequent p-values will be nominal.

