### **5 STATISTICAL ANALYSIS METHODS**

#### **5.1 General Considerations**

Unless otherwise specified, all statistical analyses will be performed on the mITT population.

In general, summary statistics (n, mean, SD, median, minimum, and maximum for continuous variables, and number and percentage of subjects in each category for categorical variables) will be provided by treatment. All summary tables will be based on the observed data unless specified otherwise. Source data for the summary tables and statistical analyses will be presented as subject level data listings.

The two-sided significance level of 5% is used for the hypothesis testing, unless specified otherwise.

Fixed sequence testing procedure will be utilized to compare the effectiveness of the treatment vs control in the following order:

Primary endpoint → Key secondary endpoint → Additional Secondary endpoints (24hr CTD → platelet transfusions → PRBC transfusions → UBPB events by class → surgical re-exploration for excessive bleeding → fatal perioperative bleeding event)

The significance for the secondary endpoints will only be considered if the primary endpoint is declared statistically significant and the p-value of the previous endpoint is less than 5%, otherwise, the testing procedure stops, and all the subsequent p-values will be nominal.

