### **5.4 Analysis of Additional Secondary Effectiveness Endpoints**

All analyses will be performed on the mITT, PP, i-CABG mITT, and i-CABG PP populations.

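### SAP 5.4.2.1 does not define a single p-value for the UDPB-by-class step of the testing sequence, and its test and apparent testing order differ from the protocol's

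*SAP*

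**What the plan says.** **Test, SAP.** Under SAP 5.4.2.1 the Clinical Events Committee (CEC) adjudicates UDPB ≥2 events. Then: "The adjudicated events will be analyzed using the Mann-Whitney U test method stratified by class", the classes being moderate (2), severe (3) and massive (4). The purpose is "to assess the risk of having different severity of bleeding events between the treatment and control group". No other variable to rank is named, and subjects without a UDPB ≥2 event are given no category.

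**Population, SAP.** Section 5.1: "Unless otherwise specified, all statistical analyses will be performed on the mITT population". Section 5.4: "All analyses will be performed on the mITT, PP, i-CABG mITT, and i-CABG PP populations".

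**Sequence, SAP.** After the primary, key secondary, 24-hour CTD, platelet and PRBC tests, Section 3.7 continues: "UDPB events by class → surgical re-exploration for excessive bleeding → fatal perioperative bleeding event". Section 5.1 repeats this order. It requires the preceding p-value to be below 5%; "otherwise, the testing procedure stops, and all the subsequent p-values will be nominal". Section 3.7 applies the same hierarchy to i-CABG.

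**Protocol.** The synopsis says: "proportions of UDPB events (by category) will be assessed via a Fisher-Freeman-Halton exact test", and Section 11.3 repeats it. For the tests after PRBC, Section 11.3 says: "further secondary endpoints will be evaluated: the proportion of fatal perioperative bleeding events, proportions of UDPB events (by category), and surgical re-exploration rates". It also says that the testing order follows the listing in the paragraph before, where these three appear in that same order. The endpoint lists in the synopsis and Section 4.3.3 run the other way: UDPB, re-exploration, fatal bleeding.

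The SAP introduction says that it is based on Version 5.1 of the investigation plan. It comments on neither difference.

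**The concern.** Stratification removes a nuisance factor so that the outcome can be compared within its levels. Here the stratifying factor is the outcome. A fixed sequence needs exactly one pre-specified p-value at each step, and this wording does not supply one at step 6.

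Two things are at stake. If step 6 has no agreed p-value, re-exploration and fatal bleeding behind it cannot be tested as confirmatory. If the test is settled only after unblinding, the choice between two documented tests can push the error at that step above 5%. The order matters as well, because a step that is planned to show no difference closes the gate to everything after it.

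**Working it through.** **Inputs.** From SAP Table 1: UDPB ≥2 in 24.3% (treatment) vs 40.5% (control), fatal bleeding 3.0% vs 3.0%, 65 per arm (Scenario 2). Two-sided 0.05 (SAP 5.1). From Protocol Section 3: severe or massive bleeding 17.7%, or 16.0% after matching. This comes from a different registry than the 40.5%. The documents do not split UDPB ≥2 into classes.

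**The plan's own figures.** No power is stated for the UDPB-by-class step. The stated primary power reproduces: simulating the Finkelstein-Schoenfeld statistic of SAP 5.2.2.1 gives 99.7% at 57 per arm (stated 99.7%) and 91.7% at 65 per arm with SD 500 (stated 92.1%). Platelets (98.0%) and PRBC (96.7%) reproduce at 57 per arm.

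**Reading 1: rank class within class strata.** The tie-corrected rank-sum variance in a stratum of N subjects (n₁ treated, n₀ control) is

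n₁n₀/12 × [(N+1) − Σ(t³−t)/(N(N−1))].

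All N subjects tie, so t = N and (N³−N)/(N(N−1)) = N+1. The bracket is zero, and so is the numerator. Z = 0/0, and there is no p-value.

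**Reading 2: one rank test per class on a yes/no indicator.** This gives three p-values and no rule for which opens the gate. Take invented counts for classes 0-1/2/3/4 of 49/13/3/0 (treatment) and 39/13/10/3 (control). The per-class p-values are 1.00, 0.041 and 0.081. Whether step 7 is opened depends on which one counts.

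**Reading 3: drop the stratification and rank ordered class in all subjects.** This gives one p-value (0.026 for the same counts), but it is not the protocol's test (Fisher-Freeman-Halton, 0.045).

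**How far the SAP's likely test and the protocol's test differ.** The share of UDPB ≥2 subjects in class 3-4 is taken as 17.7/40.5 = 0.437 or 16.0/40.5 = 0.395. The class 3:4 split is assumed at 90/10, 75/25 or 50/50. Categories are <2, 2, 3, 4, with 40,000 simulated trials per setting, 65 per arm, and Fisher-Freeman-Halton by full enumeration.

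| Setting | Rank test, all subjects | Fisher-Freeman-Halton | Smaller p-value of the two |
|---|---|---|---|
| No difference (24.3%, 32.4% or 40.5% in both arms; 18 settings) | 4.7-5.2% | 4.7-5.2% | 7.4-8.4% |
| 24.3% vs 40.5%, same class mix (6 settings) | 49% | 35-39% | – |
| As above, class 3-4 assumed 7.7% vs 17.7% of all subjects (3 settings) | 55% | 39-43% | – |

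**Order.** At 3.0%, about 65 × 0.03 = 1.95 fatal bleeds are expected per arm. With no events in one arm, Fisher's test needs six in the other:

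- 5 vs 0: p = 2 × (65·64·63·62·61)/(130·129·128·127·126) = 0.058.
- 6 vs 0: that value × 60/125 = 0.028.

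By enumeration, the test is significant in 0.41% of trials at 3.0% vs 3.0%. If the protocol's order is strict, UDPB would be reached in at most about 0.4% of trials under the planning assumptions.

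**The case against.** **The intent can be guessed.** The population statements, the stated purpose and the phrasing about risk all point to a rank test on ordered class in all subjects. That is fair, and it is why a reader who infers that step 6 simply has no p-value goes too far. That is one of three readings. What stands is that the SAP does not choose among them, and that the likeliest one departs from the protocol.

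**A test among bleeders only.** Because the sentence speaks of adjudicated events, and these are UDPB ≥2 only, a reader might infer a test restricted to those subjects, which would condition on a post-randomisation outcome. The support is weak. SAP 5.1 and 5.4 set whole analysis populations, and SAP 5.4.2.2 and 5.4.2.3 use the same idea of risk for Fisher tests that need every subject as denominator. This reading is not used in the figures above.

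**The error figure is a worst case.** It requires someone to compute both p-values unblinded and keep the smaller, with UDPB truly null after CTD and both transfusion endpoints have succeeded. The SAP also requires changes to planned analyses to be documented in the investigation report, and the mock tables, which are a separate document, may settle the test. So a reader should not take 7.4-8.4% as study-wide error.

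**The order conflict is not certain.** Protocol 11.3 chains the first five tests explicitly and presents PRBC as the end of that chain. A strict order among the last three rests on its general reference to the preceding paragraph. The protocol's endpoint lists follow the SAP's order. This stands as a qualification: the two documents need aligning, but the protocol may never have meant to gate UDPB behind fatal bleeding.

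**Conclusion.** The point holds in limited form. SAP 5.4.2.1 does not define one p-value for step 6. The protocol names a different test, and on the most natural reading of Section 11.3 the order of the last three tests differs too. Neither difference is explained.

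The reach is steps 6 to 8, and the same hierarchy in i-CABG, only when the first five tests succeed. A reader might infer that the primary result or the sample size is in doubt; neither is touched. UDPB ≥2 is already in the primary endpoint, and UDPB ≥3 and ≥4 have clear Fisher tests in SAP 5.4.2.2, although these sit outside the sequence and cannot supply step 6.

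The 7.4-8.4% error and the power figures (49% against 35-39%) rest on a class mix pieced together from two registries and on assumed 3:4 splits, so they are illustrations. The zero variance does not depend on them. The 0.4% for fatal bleeding depends only on the planned 3.0% rates and 65 per arm; that it would block UDPB also assumes a strict protocol order. Severity: minor to should-fix.

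**What to change.** Before unblinding, replace the second sentence of SAP 5.4.2.1 with:

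> UDPB class (<2, 2, 3, 4; class 2 or higher as adjudicated by the CEC; subjects without a UDPB ≥2 event counted as <2) will be compared between arms, using all subjects in each analysis population of Section 5.4, with one unstratified Fisher-Freeman-Halton exact test at two-sided 0.05. The mITT p-value is step 6 of the testing sequence, and the i-CABG mITT p-value is step 6 of the i-CABG sequence.

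This keeps the protocol's test. Pooling classes 0 and 1 is a choice made here: only UDPB ≥2 is adjudicated, and the protocol asks for a comparison by category without defining the categories, while its Table 1 has five classes.

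If the rank approach is preferred for its use of the ordering and its higher power in the table above, specify one unstratified Wilcoxon rank-sum test on the same four ordered categories, and amend Protocol 11.3 and the synopsis.

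Put one order for the last three tests in both documents. Keeping the SAP's order changes one sentence in Protocol 11.3, matches the protocol's own endpoint lists, and avoids placing a test planned with no difference ahead of UDPB.

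The cost is one SAP sentence and one protocol sentence. Any protocol change goes through the amendment process in Protocol Section 16. No new data are needed.

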##### **5.4.2.2 Supplemental Analyses**

Two supplemental analyses will be conducted using Fisher exact test on the risk of having UDPB  $\geq 3$  and UDPB  $\geq 4$  events, respectively.

The estimated rates within each group and odd ratios comparing the treatment groups will be provided along with the 95% confidence intervals.

##### **5.4.2.3 Other Categorical Secondary Effectiveness Endpoints**

The following endpoints associated with the bleeding events will be evaluated within 48 hours after the index surgery and adjudicated by CECs according to the CEC charter.

- All surgical re-exploration for excessive bleeding
- Total fatal perioperative bleeding events

The adjudicated endpoints will be analyzed using the Fisher exact test to evaluate the risk of having the events between the treatment groups. The estimated rates within each group and odd ratios comparing the treatment groups will be provided along with the 95% confidence intervals.

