H_A : For at least one component, the distribution is different between the treatment groups.

Table 3. Win Ratio Effect Size Assumptions with Power and Sample Size Estimates

n Per Group	Effect Size						Power	
	Component #1		Component #2		Component #3			
	Fatal Bleeding		UDPB (Class ≥ 2)		24hr CTD			
	Treatment Event	Control Event	Treatment Event	Control Event	Treatment Mean (SD)	Control Mean (SD)		
N=57	3.0%	3.0%	24.3%	40.5%	480 (253)	800 (253)	≥99.7%	

Notes: n = number; UDPB = Universal Definition of Perioperative Bleeding; CTD = chest tube drainage (volume [mL]).

Component #1 minimum rates of 3.0% assumed as a conservative approach.

Component #2 rates based on Russo et al. (2019), however, with a discount applied to bring the Treatment arm up to ~40% reduction on the Control arm. [14]

Component #3 rates based on Hassan et al. (2019), however, with a discount applied to bring the Treatment arm up to ~40% reduction on the Control arm. [8]

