## 2 SAMPLE SIZE AND STATISTICAL POWER CONSIDERATION

The hypothesis for the primary effectiveness endpoint will be tested using Finkelstein-Schoenfeld test (Finkelstein et al 1999). With the assumed effect sizes and variability for Scenario 1 outlined in Table 1 (Section 11.1 of the CIP), 57 subjects per arm will provide >99% power for the primary effectiveness endpoint based on Finkelstein-Schoenfeld test statistics at the two-sided significant level alpha ( $\alpha$ ) of 0.05. Taking into consideration higher than anticipated variability observed with the 24hr CTD variable, in scenario 2 we consider the same effect sizes in the 3 components and a larger variability (double of that in Scenario 1). In that instance the needed sample size is 65 per arm to achieve 92% power.

With this same sample size per arm, power for the key secondary endpoint is estimated >99.9%, and for 24-hour chest tube drainage (mL), >99.9%, based on a two-sample t-test assuming equal variance and a two-sided alpha of 0.05. Assuming unequal variances, power for comparisons of platelet transfusions (volume [mL]) and PRBC transfusions (volume [mL]), is estimated at 98.0% and 96.7%, respectively.

Allowing for ~7% dropouts, approximately 140 subjects will be randomized in a 1:1 ratio to the treatment and control arms to ensure that 130 subjects (65 per arm) will be evaluable for the primary effectiveness analysis.

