**Table 1. Effect Size Assumptions with Power and Sample Size Estimates**

Scenario	Sample size Per Group	Effect Size						Power	
		Component #1		Component #2		Component #3			
		Fatal Bleeding		UDPB (Class ≥2)		24hr CTD			
Treatment Event	Control Event	Treatment Event	Control Event	Treatment Mean (SD)	Control Mean (SD)				
1	N= 57	3.0%	3.0%	24.3%	40.5%	480 (253)	800 (253)	99.7%	
2	N=65	3.0%	3.0%	24.3%	40.5%	480 (500)	800 (500)	92.1%	

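### For fatal perioperative bleeding the SAP plans no between-arm interval on the absolute scale; at its own 3.0% rate the odds ratio is zero, infinite or undefined in about one trial in four

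*SAP*

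**What the plan says.** SAP 5.4.2.3 covers surgical re-exploration for bleeding and fatal perioperative bleeding, which "will be evaluated within 48 hours after the index surgery". The test is stated as: "The adjudicated endpoints will be analyzed using the Fisher exact test to evaluate the risk of having the events between the treatment groups". For estimation, the section gives rates by arm, and then "odd ratios comparing the treatment groups will be provided along with the 95% confidence intervals". SAP 5.4.2.2 uses the same formula for UDPB class 3 or higher and class 4: "The estimated rates within each group and odd ratios comparing the treatment groups will be provided along with the 95% confidence intervals".

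Neither section names a risk difference, a risk ratio, a method for the confidence interval, or what to report when an arm has no events. SAP 5.4.3 allows an optional time-to-event analysis but names no effect measure. Protocol 11.3 names only the exact tests for the fatal-bleeding and UDPB proportions.

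The planning rate for fatal bleeding is 3.0% in both arms (Protocol Table 3 and SAP Table 1, "Effect Size Assumptions with Power and Sample Size Estimates"). The protocol's note to its table reads "Component #1 minimum rates of 3.0% assumed as a conservative approach". SAP section 2 sizes the trial to "ensure that 130 subjects (65 per arm) will be evaluable for the primary effectiveness analysis"; its other scenario is that "57 subjects per arm will provide >99% power for the primary effectiveness endpoint".

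**The concern.** The odds ratio is the only between-arm estimate that the plan commits to for an outcome with about two expected events per arm. With counts that small, one arm will often be empty. The odds ratio then sits at 0 or infinity with a one-sided interval, or does not exist. Even with events in both arms, its interval is very wide.

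Fatal bleeding is the top tier of the primary composite and has a place in the SAP's ordered testing sequence. The plan assumes no difference on it, so the realistic reporting task is to say how large a difference in either direction the data still allow. An interval in percentage points does that directly, and none is planned.

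**Working it through.** **Inputs.** Fatal-bleeding rate 3.0% per arm (SAP Table 1). Evaluable per arm: 65 (SAP section 2, scenario 2), 57 (scenario 1), or 70 if all 140 randomized subjects count.

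**The plan's own figures.** The Finkelstein-Schoenfeld test was simulated with the statistic and variance of SAP 5.2.2.1 (3,000 trials per scenario, independent components, normal drainage volumes). Power was 99.6% at 57 per arm (SAP: 99.7%) and 91.8% at 65 per arm (SAP: 92.1%). For dropout, 130 / (1 − 0.07) = 139.8, so 140. The planning inputs are therefore used as the SAP uses them.

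**Chance of an empty arm.** Let q be the probability of no events in a given arm, q = (1 − 0.03)^n. At n = 65, q = 0.97^65 = 0.138. Then:

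- Device arm empty, control not: q(1 − q) = 0.138 × 0.862 = 11.9%. The odds ratio is 0 and has only an upper limit.
- Control arm empty, device not: also 11.9%. The odds ratio is infinite and has only a lower limit.
- Both empty: q² = 1.9%. The odds ratio is undefined.
- At least one empty: 1 − (1 − q)² = 25.7%.

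The total is 22.3% at 70 per arm and 32.1% at 57. It also depends on the true rate: at 65 per arm it is 46.6% if the rate is 2% in both arms and 7.0% if it is 5%.

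**What each measure gives at 65 per arm** (device vs control; exact conditional interval for the odds ratio, Newcombe interval for the risk difference in percentage points):

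| Events | Odds ratio (95% CI) | Risk difference (95% CI) | Fisher p |
|---|---|---|---|
| 2 vs 2 | 1.0 (0.07 to 14.2) | 0 (−7.8 to +7.8) | 1.00 |
| 0 vs 2 | 0 (0 to 5.3) | −3.1 (−10.5 to +2.9) | 0.50 |
| 2 vs 0 | infinite (0.19 to infinity) | +3.1 (−2.9 to +10.5) | 0.50 |
| 0 vs 0 | undefined (0 to infinity) | 0 (−5.6 to +5.6) | 1.00 |
| 0 vs 5 | 0 (0 to 1.06) | −7.7 (−16.8 to −0.6) | 0.058 |

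**The other outcomes in these sections.** Protocol section 3 cites 17.7% for UDPB class 3 or higher in patients operated on within two days of the last dose. At that rate q = 0.823^65 = 3.2 in a million, so the chance that either arm is empty is about 6 in a million. The documents give no planning rate for re-exploration or for UDPB class 4, so no figure can be put on those.

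**Smaller planned sets.** SAP 5.4 repeats these analyses in the isolated-CABG populations, whose size is not stated. If they held 40 to 60 per arm (an assumption), the chance of at least one empty arm at 3% would be about 50% to 30%.

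**The case against.** A reader might infer that the odds ratio is unusable in one trial in four. The documents do not support that. An odds ratio of 0 is a finite value, and an exact method gives it a valid upper limit (5.3 for 0 vs 2). It is infinite or undefined only when the control arm is empty, which has probability 13.8%.

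A reader might also extend the figure to every outcome in SAP 5.4.2.2 and 5.4.2.3. That fails for UDPB class 3 or higher on the protocol's own cited rate, and it cannot be assessed for the two outcomes without a stated rate.

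Three further points have force:

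- The arm rates are reported, apparently with intervals, and counts are tabulated. A reader can subtract the rates and work out an interval. What is missing is a prespecified one.
- The risk-difference interval is wide too: ±7.8 points against a 3% base rate is not precise. The shortage of events drives this, and no choice of scale removes it. The gain is an interval with two finite limits in every table, in units that can be weighed clinically.
- A Newcombe interval can disagree with Fisher's test. For 0 vs 5 it excludes zero while p = 0.058; the exact odds-ratio interval, 0 to 1.06, agrees with the test. This is a reason to keep the odds ratio and to label the risk difference as descriptive. It is not a reason to leave the risk difference out.

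No formal decision turns on this. Fatal bleeding is the last of eight steps in the SAP sequence, Fisher's test copes with empty cells, and the primary endpoint compares pairs of subjects without using an odds ratio.

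**Conclusion.** The point holds as a modest estimation and reporting gap for fatal perioperative bleeding. At the plan's own inputs, the sole between-arm estimate is 0, infinite or undefined in 25.7% of trials (22.3% to 32.1% across 70 to 57 per arm), and no absolute-scale interval is planned to bound a neutral result. The figure assumes a true rate of 3.0% in both arms and independent subjects; a lower rate makes it worse and a higher rate makes it better. Error control, power and the primary analysis are unaffected. This is an improvement worth making, not a flaw that threatens the trial's conclusion.

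**What to change.** In SAP 5.4.2.3, and for consistency in 5.4.2.2:

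1. Add the risk difference, device minus control, with a Newcombe or Miettinen-Nurminen 95% interval, choosing one method in advance.
2. State that this interval is descriptive and that Fisher's exact p-value alone decides significance in the testing sequence. Without that statement, a table such as 0 vs 5 events could be read two ways.
3. Keep the odds ratio in every table, specify an exact 95% interval for it, and report it as not estimable when neither arm has an event. It should not be dropped whenever a cell is zero: that would make reporting depend on the data and discard a valid limit.

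The cost is about two sentences per section and one extra column in the output tables. No new data are needed, and alpha and power do not change. The remaining downside is occasional disagreement at the margin between the risk-difference interval and Fisher's p-value, which item 2 handles.
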